of other existing methods such as invasive methods.[47] The Esophageal Cooling Device (shown in Figure 1 and Figure 2) is a multichambered silicone heat exchanger that is placed in the esophagus to provide highly efficient heat transfer to/from a patient while simultaneously maintaining access to the stomach to allow gastric suctioning, decompression, and drainage, as usually performed in such patients in emergency departments, operating rooms, and intensive care units.

[figure not shown]

Figure 1. Photograph of the Esophageal Cooling Device (ECD).

The esophagus is in close proximity to blood flow from the heart and great vessels, and the Esophageal Cooling Device is designed to take advantage of this heat exchange environment. The Esophageal Cooling Device's ability to decompress the stomach and avoid distention of the esophagus away from the device ensures good contact with the esophageal mucosa, and thus maximizes heat transfer from the patient. The Esophageal Cooling Device replaces the standard orogastric tube which is placed in the target patient population as a routine standard of care, is made of standard medical-grade silicone, and is generally similar in size and shape to the orogastric tubes currently used. Initial mathematical and animal studies have shown strong support for the efficacy and safety of the Esophageal Cooling Device.[47-49]

[figure not shown]

Figure 2. The Esophageal Cooling Device (ECD) shown in place in the esophagus (replacing the routine gastric tube placed in the target population as a standard of care), and located behind the trachea (containing the endotracheal tube which is placed in the trachea routinely to provide ventilation in the target patient population).

Study design:

Prospective, interventional study evaluating the feasibility and safety of the Esophageal Cooling Device in 15 patients suffering from traumatic brain injury and treated with targeted temperature management. Comparison of outcomes will be made to historical controls, and analysis will utilize a non-inferiority design.

Primary outcome:

Time to initiation of targeted temperature management, as measured from the time a decision is made to begin targeted temperature management, to the time the esophageal cooling device is in place.

Secondary outcomes:

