Secondary performance outcomes include the feasibility of inducing, maintaining, and rewarming patients from targeted temperature management using the Esophageal Cooling Device. Specifically, cooling rate, rewarming rate, and the percent of time during the goal-temperature maintenance period within 1°C of goal temperature (typically 33°C, but with some centers using anywhere from 32°C to 36°C) will be measured.

Secondary safety outcomes include evaluation of adverse events including the following: cardiac arrhythmias, severe bradycardia, myocardial infarction/re-infarction, dysphagia, odynophagia, aspiration pneumonia, non-aspiration pneumonia, reflux, esophageal injury, and esophagitis.

Specific definitions of adverse events and the methods used to identify and diagnose each during the treatment and 30-day follow-up phases are as follows:

- Cardiac arrhythmias - recording of atrial or ventricular arrhythmias during course of treatment.
- Severe bradycardia - heart rate < 30/min and necessitating pacing and cessation of TH.
- Myocardial infarction - universal definition of myocardial infarction as per the joint ESC/ACCF/AHA/WHF Task Force for the Redefinition of Myocardial Infarction.[50]
- Dysphagia - report from patient of difficulty in swallowing for more than 24 hours after cessation of device use, diagnosed with a Modified Barium Swallow Study, Videofluoroscopic Swallow Study, or patient self-report.
- Odynophagia - report from patient of pain with swallowing for more than 24 hours after cessation of device use, diagnosed by subjective patient sensation.
- Aspiration pneumonia - demonstration by chest X-ray of evidence of aspiration pneumonia, as diagnosed by treating physician, within 24 hours of cessation of device use.

- Non-aspiration pneumonia - demonstration by chest X-ray of evidence of pneumonia within 24 hours of cessation of device use that is diagnosed by the treating physician as non-aspiration pneumonia.
- Reflux - report of symptoms from patient within 3 days of recovery, with diagnosis via esophageal pH monitoring or endoscopy.
- Esophageal injury - evidence of traumatic and/or ischemic esophageal injuries diagnosed by gastroenterologist evaluation via esophagogastroduodenoscopy as warranted or indicated, and describing the absence of necrosis or not according to the Zargar classification used for caustic injuries within 3 days of recovery .

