Written informed consent will be obtained from each patient's next of kin or patient's legal representative before inclusion. Surviving patients without severe neurological sequels will give their written informed consent. When a patient has recovered, and is able to do so, he/she has to sign the informed consent form personally.

This study will be conducted according to the principles of the Declaration of Helsinki (as amended October 2013) of the World Medical Association. The protocol will be submitted and approved by the local Ethics Committee of the institution.

Randomization:

Randomization: none

Esophageal Cooling Device:

The placement of the Esophageal Cooling Device will follow standard recommendations as per Instructions for Use. The Esophageal Cooling Device will be connected to the appropriate console (Meditherm III, Blanketrol II, or Blanketrol III).

Other treatments:

Standard treatments for traumatic brain injury will follow local guidelines. Fluid and other management is left at the discretion of the attending physician.

Data collection:

All clinical and biological parameters will be recorded according to the Utstein-style recommendations for reporting resuscitation outcomes.[51] Neurologic outcome will be assessed according to the Cerebral Performance Category (CPC) score.[52] Initial temperatures will be measured via a tympanic or naso-pharyngeal temperature sensors in the prehospital field if available, or by other means used as standard of care. Continuous temperature measurement (specifically during cooling, maintenance, and rewarming) will be measured by bladder temperature sensors or rectal temperature sensors, and arterial temperature monitoring if available. Time of ECD placement in a patient will be recorded; the potential side effects (see above) will be recorded throughout the entire study..

Study assessments and procedures

Screening on Day 1

This visit includes the primary diagnostic procedures and the verification of the eligibility criteria. Subjects are eligible for the study will undergo the following procedures at this visit:

- Written informed consent (the form will be signed by a patients or legally acceptable representative);
- Previous medical history and co-morbidities;
- Physical examination including body weight, height and BMI, general appearance, heart, lungs, abdomen and extremities examinations;
- Demographics;
- Smoking habits;
- Alcohol consumption;
- Inclusion/exclusion criteria;

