current standard (cooling blankets or evaporative cooling). For the endpoint of percent of time over the study period within 1°C of goal temperature (33°C), the treatment effect of the active control is large, since non-treatment results in essentially no attainment of goal temperature. An estimate of effect of the active comparator (M_1) is therefore greater than would be acceptable to use as a base for a non-inferiority margin. Consequently, a more restrictive non-inferiority margin (M_2) is then proposed of 15% (i.e., if the standard maintains goal temperature $+\/-1^\circ\text{C}$ for 60% of the time, and the ECD maintains goal temperature $+\/-1^\circ\text{C}$ for 85% of the time, the lower bound of the 95% CI on the difference between percent time at goal temperature between standard and test device is greater than 70%). Setting the type I error rate to 5%, for an alpha of 0.05, and a power of 80%, for a beta of 0.2, yields a sample size estimate of 15 patients in the study (with another at least 15 patients coming from historical controls with available esophagogastroduodenoscopy evaluation).

Data analysis: as recommended by current FDA guidance documents, both per-protocol (as-treated) and intent-to-treat analyses will be performed.[53] Lower 95% confidence limit for difference between groups must exclude the non-inferiority margins for primary end point in both efficacy and safety.

Abbreviation

ACT - Advanced Cooling Therapy

AE – adverse event

BNP - brain natriuretic peptide

ECG - electrocardiogram

GCS – Glasgow Coma Score

CPC - Cerebral Performance Category

CT – computed tomography

ECD - Esophageal Cooling Device

ECLS - Extra-Corporeal Life Support

EEG – electroencephalogram

LBBB - left bundle branch block

MAP – mean airway pressure

MRI - Magnetic Resonance Imaging

Protocol No ACT TBI-01

Version No 2.0 dated on 08-Dec-2014

OTC – over-the-counter

ROSC - Return of Spontaneous Circulation

SAE – Serious Adverse Event

SAPS – Simplified Acute Physiology Score

SOFA – Sequential Organ Failure Assessment

SSEP - Somatosensory evoked potentials

STEMI - ST-elevated myocardial infarction

TH - Therapeutic Hypothermia

References:

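### Safety is put into a between-group test against historical controls, but adverse events are ascertained differently in the two groups and the bias can run either way

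*Combined protocol and SAP*

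**What the plan says.** The Study design section states that "Comparison of outcomes will be made to historical controls, and analysis will utilize a non-inferiority design". The Data analysis paragraph of the Statistical analysis section sets the decision rule: "Lower 95% confidence limit for difference between groups must exclude the non-inferiority margins for primary end point in both efficacy and safety". The controls enter through the sample size for the secondary outcome: 15 ECD patients, "with another at least 15 patients coming from historical controls with available esophagogastroduodenoscopy evaluation". Their cooling is described there as blankets or evaporative cooling.

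The ten adverse events are defined under Secondary outcomes. Dysphagia is a "report from patient of difficulty in swallowing for more than 24 hours after cessation of device use". Odynophagia is a "report from patient of pain with swallowing for more than 24 hours after cessation of device use". Both pneumonias are also counted from the end of device use. For ECD patients, Data collection says that "the potential side effects (see above) will be recorded throughout the entire study". Study assessments and procedures adds daily recording of adverse events on days 1-7 of an ICU stay. EGD is recorded only if it was performed.

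For controls the plan gives no data source, time anchor, abstraction rule or adjudication. It gives no margin for any adverse event.

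**The concern.** A between-group safety test needs the same event to be looked for in the same way in both groups. Here the method of looking depends on the group and on the event. A control who never had the device has no end of device use from which to count. A symptom such as pain on swallowing exists for a control only if someone wrote it down at the time. An esophageal lesion exists only if someone looked with an endoscope, and the two groups differ in who was looked at.

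Safety is one of the two stated aims of the study. If the rule were applied as written, a finding of non-inferior safety, or a failure to show it, could arise from ascertainment alone. Supplying the missing safety margin would not cure this.

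**Working it through.** **1. The plan's own figure.** The 15 per group reproduces, but it sizes percent of time at goal temperature, not safety. The inputs from Statistical analysis are 60% and 85%, margin 15 points, alpha 5%, power 80%:

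n = (1.645 + 0.842)² × (0.60×0.40 + 0.85×0.15) / (0.25 + 0.15)² = 6.18 × 0.3675 / 0.16 = 14.2, rounded up to 15 (one-sided 5%).

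At one-sided 2.5%, which matches a two-sided 95% interval, it is 7.85 × 0.3675 / 0.16 = 18.03, rounded up to 19. No event rate, margin or sample size is given for adverse events.

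**2. Definitions side by side (Secondary outcomes).**

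| Event | Timed from end of device use | Patient report | EGD |
|---|---|---|---|
| Arrhythmia | no | no | no |
| Severe bradycardia | no | no | no |
| Myocardial infarction | no | no | no |
| Dysphagia | yes | yes, or swallow study | no |
| Odynophagia | yes | yes | no |
| Aspiration pneumonia | yes | no | no |
| Non-aspiration pneumonia | yes | no | no |
| Reflux | no (recovery) | yes, plus pH monitoring or endoscopy | possible |
| Esophageal injury | no (recovery) | no | yes, if indicated |
| Esophagitis | no (recovery) | no | yes, if indicated |

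Four are device-timed, three involve patient report, and five fall under one or the other. Two more rest on EGD. The remaining three can be scored from routine records.

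**3. Size if symptoms are missed in controls.** With true risk p in both groups and capture c_E (ECD) and c_C (control), the spurious difference is p × (c_E − c_C). Assume p = 30%, c_E = 100% and c_C = 50-70%; none of these is in the documents.

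- c_C = 50%: 0.30 × 0.50 = 15 points (30% v 15%).
- c_C = 70%: 0.30 × 0.30 = 9 points (30% v 21%).
- 95% half-width for 30% v 15% at 15 per group: 1.96 × √(0.30×0.70/15 + 0.15×0.85/15) = 1.96 × √0.0225 = 0.29.

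**4. Effect on the decision, in both directions.** All outcomes for 15 v 15 were enumerated. Non-inferiority was declared when the Newcombe 95% upper limit for ECD minus control was below 15 points. That margin is borrowed from the temperature endpoint, since none exists for safety.

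| True ECD / control risk | Capture ECD / control | Expected observed difference | Chance of declaring non-inferiority |
|---|---|---|---|
| 20% / 20% | 100% / 100% | 0 | 17% |
| 20% / 20% | 100% / 75% | +5 points | 10% |
| 20% / 20% | 100% / 50% | +10 points | 6% |
| 20% / 20% | 100% / 25% | +15 points | 2% |
| 20% / 20% | 50% / 100% | −10 points | 46% |
| 40% / 20% | 100% / 100% | +20 points | 1% |
| 40% / 20% | 50% / 100% | 0.40×0.50 − 0.20 = 0 | 17% |

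The rows with 50% ECD capture stand for the endoscopic events: every control has an EGD, and only some ECD patients do. In the last row a true doubling of risk disappears from the expected difference.

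**5. Which limit.** For adverse event risk taken as ECD minus control, the limit that matters is the upper one. The plan names the lower limit and does not define the direction of a safety difference.

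**The case against.** Much of the safety set can be compared. Arrhythmia, severe bradycardia and myocardial infarction are neither device-timed nor patient-reported. The pneumonias rest on X-ray and physician diagnosis and need only a common anchor such as the end of cooling. Reflux requires pH monitoring or endoscopy as well as symptoms, and dysphagia can be diagnosed by swallow study. All of this stands. A reader might infer that none of the ten events can be scored alike in controls; the definitions do not support that.

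The rule is also loosely worded. It speaks of the primary end point in efficacy and safety, whereas the ten events are secondary outcomes. That leaves doubt about which events it covers. Even so, the Study design statement covers outcomes generally, and choosing controls by EGD makes little sense unless esophageal safety is to be compared.

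The illustration assumes full capture in ECD patients, which is generous. Symptom reports need a patient who has recovered enough to give them, and no scheduled swallowing questionnaire appears. Lower ECD capture would shrink the spurious excess or reverse it. The 9-15 points are also smaller than the 29-point half-width, so imprecision is at least as large a problem as bias. Both objections stand. They limit what the figures show, but they do not make the comparison interpretable.

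**Conclusion.** The point holds in this form: the planned safety comparison is not interpretable, because ascertainment in controls is unspecified and differs from that in ECD patients by event. For the patient-reported symptoms the likely bias is against the ECD. For esophageal injury and esophagitis it may favour the ECD and hide harm.

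Two stronger readings are not supported. One is that controls are always undercounted; the selection of controls for EGD contradicts that for the endoscopic events. The other is that an observed difference would reflect record-keeping and not harm. It would mix ascertainment, case mix, chance and harm, and the plan offers no way to separate them.

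The sizes rest on assumed risks, assumed capture fractions and a borrowed margin. They show only that unequal capture can move the difference by as much as 15 points either way. The lack of a control anchor, source and abstraction rule comes from the text and needs no assumption.

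**What to change.** In Data analysis, remove safety from the between-group margin rule and state the following in its place:

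- Adverse events are reported for ECD patients only, as counts with exact (Clopper-Pearson) 95% confidence intervals. With no events in 15 patients, for example, the upper limit is 1 − 0.025^(1/15) = 21.8%.
- For the endoscopic events, the report gives the number of ECD patients who had an EGD beside the count.
- Any comparison with controls is labelled descriptive. It is limited to events in routine records in both groups: arrhythmia, severe bradycardia, myocardial infarction, and the pneumonias with one window from the end of cooling for both groups.
- Patient-reported and EGD-dependent events (dysphagia, odynophagia, reflux, esophageal injury, esophagitis) are left out of that comparison. A common time window alone would not remove the imbalance in who had an EGD.

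The cost is a short edit to the analysis section and, if the descriptive comparison is kept, a stated control source and abstraction rule. The sponsor gives up a comparative safety claim that these data cannot support.

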- Esophagitis - evidence of esophageal inflammation diagnosed by gastroenterologist evaluation via esophagogastroduodenoscopy if warranted or indicated, and as defined by Savary-Miller and staged from 1 to 4 according to the severity of the disease within 3 days of recovery.

A serious adverse event (SAE) is defined as any adverse event that:

- Results in death
- Is life threatening
- Requires hospitalization or prolongation of existing hospitalization
- Results in persistent or significant disability or incapacity
- Is a congenital abnormality or birth defect

Patient population:

Patient population will consist of 15 patients suffering from traumatic brain injury, in whom the treating clinician has determined that targeted temperature management will be initiated.

Duration of patient's participation in the study

The patient's duration of the participation should be considered as follows:

- From signing of consent form by patient's legal representative and until 30 days if the patient has recovered within 30 days from the consent's signature and is able to sign the ICF personally;
- From signing of consent form by patient's legal representative and until the patient's recovery – patient's ability to sign the consent form (either a full or at least sufficiently partial neurologic recovery that allows the patient to awaken, function, understand conversation, ability to sign personally);
- From signing of consent form by patient's legal representative to patient's death

Inclusion criteria:

Adult patients (age 18 years and over)

Exclusion criteria:

- Patients with known esophageal deformity or evidence of esophageal trauma (for example, known esophageal varices, cirrhosis, history of esophagectomy, previous swallowing disorders, achalasia, etc.).
- Patients with known ingestion of acidic or caustic poisons within the prior 24 hours.
- Patients with less than 40 kg of body mass.
- Patients known to be pregnant.
- Terminal disease or “do not resuscitate order” that could lead to early-onset therapeutic withdrawal (<48 hours after collapse).
- Unstable hemodynamic conditions (defined as intractable severe cardiogenic shock or ECLS requiring) that could lead to multi-organ failure and early-onset death (<48 hours after collapse).
- Pre-existing severe conductive disorder requiring pacing.

Informed consent and ethical considerations:

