After the first 24 hours from the admission of the patient to the hospital Simplified Acute Physiology Score (SAPS) III will be measured.

Daily during day 1-7 if ICU stay the following procedures and assessments will be performed and recorded in the CRFs:

- Sequential Organ Failure Assessment (SOFA) scores;
- GCS scores;
- Pupillary and corneal reflex check;
- Highest body temperature;
- Highest dose and type of vasopressor/inotropic medication;
- The need for pacing;
- Intracranial pressure monitor pressures will be recorded (if measured);
- Recording of a need for mechanical circulatory assistance;
- Mechanical ventilation (if necessary);
- Recording of daily net fluid balance;
- Recording of adverse events;

Daily from day 8 to ICU discharge or day 14 the following records will be made:

- Patient comatose (yes or no);
- Mechanical ventilation (yes or no);
- Renal replacement therapy (yes or no);
- Presence of pneumonia (aspiration/non-aspiration) and sepsis (yes or no)

CPC should be assessed and recorded daily with the last recording being either at discharge, or at the 30 day time point.

Daily from day 1 to day 14 “do not attempt resuscitation order” should be recorded in the CRFs.

Based on investigator’s discretion, the following procedures may be performed if a decision is being contemplated for withdrawal of patient care”:

- Results and time of SSEP, if performed (n20 present bilaterally/n20 present unilaterally/n20 absent);
- Results and time of EEG, if performed.

At ICU discharge or 30 days from admission the following procedures will be recorded if performed (only CPC and GCS are mandatory):

- EEG, MRI, CT (if performed)
- CPC and GCS;

- Esophagogastroduodenoscopy (if performed)

Throughout the entire study:

- Concomitant medications;
- Adverse events

Statistical analysis

Sample size for primary outcome is calculated with an assumption of time to initiate cooling being approximately 5 minutes, with standard deviation of 4 minutes for the esophageal cooling device, and 20 minutes, with standard deviation of 15 minutes, for alternative devices. A power of 80%, and alpha of 5%, yields a sample size of 14 patients (with an equivalent size of historical controls). Sample size for secondary outcome is calculated for a non-inferiority test against the

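### The primary time has no value when ECD placement fails, and no rule says how the promised intent-to-treat analysis treats such a patient

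*Combined protocol and SAP*

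**What the plan says.** The Abstract and the Primary outcome section give the same definition. The clock starts at the decision to begin targeted temperature management (TTM) and runs "to the time the esophageal cooling device is in place". The outcome is labelled as time to initiation of TTM, but what is measured is time to device placement.

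Patients enter before placement. Under Patient population they are those "in whom the treating clinician has determined that targeted temperature management will be initiated", and the consent section requires consent before inclusion. Neither depends on the device going in.

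Under Data collection, "Time of ECD placement in a patient will be recorded". Neither that section nor Study assessments and procedures lists failed attempts or the start time of another cooling method.

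The Data analysis paragraph under Statistical analysis promises that "both per-protocol (as-treated) and intent-to-treat analyses will be performed". It defines neither set. The protocol contains no value, censoring rule, imputation, replacement rule or sensitivity analysis for a patient in whom the ECD is never placed.

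**The concern.** An intent-to-treat analysis should include every enrolled patient, whether or not the device worked. Here the endpoint exists only if placement succeeds. The label and the measurement agree while the device goes in and part company when it does not: a patient switched to another method has a TTM start time but no ECD placement time.

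Three things are at stake. First, if failures are left out, the ECD mean describes successful placements only and is too short as a summary of all patients in whom the device was tried. Second, the intent-to-treat analysis gives no protection against this, because it has nothing to analyse for a failed placement. Third, the information may be unrecoverable. Temperatures are taken hourly from consent, which is too coarse to recover a start time when the planned ECD mean is 5 minutes.

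Feasibility is also a stated aim, yet no listed outcome counts how often placement succeeds.

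**Working it through.** **1. The plan's own sample size.** Statistical analysis assumes "time to initiate cooling being approximately 5 minutes, with standard deviation of 4 minutes for the esophageal cooling device". Its planned control mean is 20 (SD 15). The other inputs are alpha 5% (sides not stated), power 80% and equal groups.

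n per group = (4² + 15²) × (1.960 + 0.842)² / 15² = 8.4, so 9 two-sided. The one-sided result is 6.6, so 7. Exact t calculations give 10 (pooled) or 11 (Welch) two-sided and 8 one-sided. The stated 14 is not reproduced directly. It is reached with SD 15 in both groups and a one-sided t test, which the text does not say. It is conservative for the stated SDs (power about 92% to 95% two-sided), and nothing below depends on it. It contains no stated allowance for failed placements.

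**2. A failed placement traced through the plan.**

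| Step | Outcome for this patient |
|---|---|
| Enrolled? | Yes, entry rests on the decision to start TTM |
| Primary time defined? | No, the end event never occurs |
| Placement time recorded? | None exists |
| Alternative start time recorded? | Not a listed item |
| Rule in the analysis text? | None |

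**3. Effect on the ECD mean.** Let k of 15 placements fail and count each failure as T minutes, with successes at the planned 5:

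mean = [(15 − k) × 5 + k × T] / 15

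Both k and T are assumptions. T = 25 is built from the plan's own figures (a 5-minute attempt, then a 20-minute alternative). T = 60 is a deliberately long value.

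| k | Failures dropped (expected) | T = 25 | T = 60 |
|---|---|---|---|
| 1 | 5.0 | (70 + 25)/15 = 6.3 | (70 + 60)/15 = 8.7 |
| 2 | 5.0 | (65 + 50)/15 = 7.7 | (65 + 120)/15 = 12.3 |
| 3 | 5.0 | (60 + 75)/15 = 9.0 | (60 + 180)/15 = 16.0 |

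Dropping failures understates the mean by (T − 5)/15 per failure: 1.3 minutes at T = 25 and 3.7 at T = 60.

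For the all-patient mean to reach the planned control mean of 20, T must be [300 − (15 − k) × 5]/k. That is 230 minutes for one failure, 117.5 each for two and 80 each for three.

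**4. Chance of at least one failure in 15.** 1 − (1 − f)^15 gives 26%, 54% and 79% at assumed failure rates f of 2%, 5% and 10%.

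**5. Effect on the comparison.** This used 40,000 simulated trials of 15 against 15, with lognormal times at the planned means and SDs and a two-sided Welch test. In the T = 25 column, attempt and alternative times were drawn at random and average 25 minutes.

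| k | Failures dropped | T about 25 | T = 60 |
|---|---|---|---|
| 1 | 99% | 94% | 54% |
| 2 | 99% | 83% | 4% |

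The Welch test is a stand-in. The plan requires that "Lower 95% confidence limit for difference between groups must exclude the non-inferiority margins for primary end point in both efficacy and safety", but gives no margin in minutes for the primary time.

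**The case against.** The strongest reply is that the plan is silent and does not state an exclusion. A time to initiation could be censored, ranked or imputed, and nothing says that failures are removed. That stands. A reader might infer that the plan excludes failures, or that it would report 5.0 minutes whatever happened. The documents support neither: 5 minutes is a planning assumption, and dropping failures is only what follows if nobody adds a rule.

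A reader might also infer that the two analysis sets are bound to be identical. They need not be, since neither is defined and they could differ for other reasons, such as eligibility violations. What can be said is narrower: on the primary time, neither can use a failed placement.

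The size is also open to challenge. The protocol describes the device as close in size and shape to ordinary orogastric tubes, and the exclusion criteria remove known esophageal abnormality, so failures may be rare. Sixty minutes lies (60 − 20)/15 = 2.7 SD above the plan's mean for alternative devices. With one or two failures and a prompt switch, the planned contrast of 5 against 20 would usually survive. These points stand, and they limit the weight of the finding.

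Finally, it is tempting to conclude that the ECD will look faster than the controls when it is not. The documents do not support that. They do not say where the clock stops for historical controls, who have no ECD, and the controls' times may likewise exist only where cooling began.

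The reply does not supply a primary value for the failed patient. A blank placement time might reveal a failure, but it would not give the time at which cooling began.

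**Conclusion.** The point holds in a limited form. As defined and recorded, the primary time conditions on device success, and the plan gives the promised intent-to-treat analysis no way to include a failed placement. This goes beyond a missing handling rule, because following the listed data collection could lose the time needed to repair it.

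If failures drop out, the ECD mean is biased towards faster times, by about 1.3 minutes per failure in 15 at 25 minutes or 3.7 at 60. One or two failures leave the mean well short of 20 in either case, although power in the stand-in test falls sharply at 60. The failure counts, the times assigned to failures and the lognormal shape are all assumptions. The direction and size of any net bias against the controls are unknown. The change should be made before enrolment, but the documents do not show that the primary conclusion would be overturned.

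**What to change.** - **Intent-to-treat time:** define it as decision to start of cooling by whatever method is finally used. Define the intent-to-treat set as all enrolled patients.
- **Controls:** apply the same clock end to the historical controls.
- **Data collection:** record failed or abandoned attempts and the start time of any alternative method.
- **Cooling never starts:** assign the worst rank in a pre-specified rank-based comparison.
- **Feasibility:** report the proportion successfully placed with an exact 95% interval. Even 15 of 15 would give a lower limit of 0.025^(1/15) = 78%.
- **Per-protocol:** keep the success-only time to ECD placement, labelled as such.

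The cost is one added time stamp, a matching abstraction from control records that may not hold a clear start time, and a possibly less favourable ECD time. The sample size text should name the rank test. Dividing the two-sided t results of 10 and 11 by 0.864, an approximate allowance, gives 12 and 13, so the planned numbers need not rise on the stated assumptions. The change concerns measurement and analysis only and does not alter patient management.
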